8.4.4 Selection of Doses in the Clinical Trial

8.4.5 Dose selection is based on previous clinical experience.

In the Phase IIa-ACE114622-Study with patients with acute respiratory distress syndrome (not in patients with COVID-19) dosing was 0.4 mg/kg BID over three consecutive days. The dose of APN01 in that study was sufficient to observe biological effect in enrolled patients, as evidenced by decreased plasma ang-II and increased plasma ang1-7 and ang1-5. Moreover, decreases in plasma IL6 and increased SP-D and a trend to lower plasma IL-6 were observed in patients assigned to the study drug, further indicating effect on biological endpoints potentially relevant to ARDS. Regarding the dosing schedule, the half-life of rhACE2 is thought to be 9.6 hours, such that twice daily dosing seems reasonable.

The dose selected was largely based on previous experience with the drug, and more precisely on the study performed by Khan et al [8]. In addition, based on previous study findings no drug accumulation was observed with repeated dose administrations (either for 3 or 6 days; (Figure 15 of IB v 11.0). On this basis it seemed rational and safe to extend treatment duration to 7 days, as it appears that 7 days is the critical period for a potential recovery of lung functions in ARDS patients [9,10, 11]

The study by Khan gave drug for only 3 days because the goal of the study was different; 3 days of dosing was felt to be sufficient to assess the basic pharmacology of the compound, initial safety in patients with ARDS, and possibly demonstrate a physiological effect. In this study, our goal is longer term outcomes.

Looking to the antiviral activity described in Monteil et al (Cell, In Press) the virus can infect and replicate in human capillaries, and kidneys which likely explains shedding of the virus in these organs, potentially leading to multi-organ failure. While, it might be possible that a higher dose would be more effective in antiviral drug activity, the drug will be given to patients with varying degrees of viral load. In clinical practice during this pandemic, it is not possible to quickly measure the viremic viral load, and in fact many patients are not viremic. As such, we thought that from a safety perspective the dose given in the previous clinical trial would be the most appropriate for this Phase 2 trial.

8.4.6 Blinding and Unblinding

The entire study team will be blinded except for an unblinded pharmacist or an unblinded team member (including team members involved in the IMP preparation, unblinded statisticians and DSMB members involved in DSMB, unblinded data managers involved in generation and the upload of treatment listings to eCRF). IMP will be provided to the pharmacy or unblinded team in an unblinded manner. The PI will inform the pharmacist or unblinded member of the study team about the randomization of a new subject. The pharmacist or unblinded member of the study team will ascertain the treatment arm from the eCRF and provide the PI with the blinded treatment. In case of an emergency, patient treatment may be unblinded directly in the eCRF. The right to unblind treatment in the eCRF assigned to a given user role. Unblinding is performed by opening the patient in the eCRF and clicking the “Emergency unblinding” link to activate the unblinding workflow. The time, date and reason for unblinding are captured in the eCRF. In addition, the unblinding will be documented in the respective “unblinding form”. Unblinding should be restricted to cases of emergency where knowledge of thy type of treatment is considered necessary for adequate treatment of the patient. The sponsor must be notified about any patient unblinded immediately. Breaking of the emergency code leads to the exclusion of the respective patient.

The randomization list will be exported and provided to statistician as part of the final data transfer. The randomization list will be archived as part of the final database archival package.

8.4.7 Prior and Concomitant Therapy

Prohibited treatment: Patients receiving ACE inhibitors, or renin inhibitors

NOTE: angiotensin receptor blockers are not prohibited.

Concomitant treatment: Any concomitant treatment given for any reason during the course of the study must be recorded on the eCRF and in the patient’s medical records, including dosage, start and stop dates and reason for use.

8.4.8 Treatment Compliance

8.4.8.1 Enrolment to the Clinical Trial

A patient will only be enrolled in the trial if all inclusion and none of the exclusion criteria are met. A patient will only be admitted to the clinical trial if the ICF has been signed and all inclusion and none of the exclusion criteria are met. Should there be any doubts as to the state of health, a patient will not be admitted to the clinical trial.

8.4.8.2 Patient Identification

The PI of each site will keep a record relating the patient numbers and the names of all patient that have given their informed consent, to allow easy checking of data in patient files, when required. This record will also include the date of the patient’s enrolment and completion, as well as patients who could not be included in the study for whatever reason.

8.4.8.3 Early Termination

All enrolled patients who discontinue early, or withdraw from the clinical trial will have the follow-up assessments and procedures completed for their safety as outlined in Table 1. Patients who discontinue early or withdraw from the clinical trial will not be replaced as long as 200 patients complete the study according to the protocol.

In some cases, it may be necessary for patients to return to the study site or will be contacted for a phone visit or in-home visit (in Russia) for additional care, confinement, and/or follow-up. Circumstances in which this may be necessary are:

- Follow-up on abnormal laboratory evaluations
- Follow-up on an ongoing AE at the final visit (day 28) and or final phone visit

All additional safety follow-up visits will be at the discretion of the investigator, the PI and the Sponsor.

8.4.8.4 Unscheduled Visits

Unscheduled visits may be performed at any time during the clinical trial. Depending on the reason for the unscheduled visit (e.g., AE, abnormal laboratory values, ECG), appropriate assessments will be performed based on the judgment of the investigator. Results of the assessment and any changes in concomitant treatment will be recorded in the eCRF. After an unscheduled visit, the regular scheduled visits must continue according to the planned visit and assessment schedule.

8.5 Efficacy and Safety Variables

8.5.1 Efficacy and Safety Measurements Assessed and Flow Chart

Details regarding scheduled assessments and procedures to be conducted in this clinical trial are provided below. For detailed assessment schedules refer to Table 1.

8.5.2 Appropriateness of Measurements

8.5.2.1 Screening Procedures

Written, signed, and dated informed consent from the patients prior to the performance of any clinical trial related procedures must be obtained by an investigator. A copy of the signed consent form and the information sheet must be given to the patient for their records after signature and before enrollment.

The time period between start of screening procedures and start of treatment must not exceed 24 hours. In case the required screening procedures take less time, randomization and start of treatment could be performed also on the same day then screening. Pre-dose events other than biomarker sampling and vital signs do not need to be performed if randomization and screening are on the same day. The following events will be performed: check of inclusion and exclusion criteria, obtaining medical history and demographics, score assessment of WHO's 11-point scale, PCR analysis, vital signs, physical examination, serum or urine pregnancy test, lab assessments, ECG, assessment of respiratory condition, mSOFA-score.

See Table 1 for a complete list of screening procedures to be performed.

Only an authorized and trained investigator may decide on the eligibility of the patient.

8.5.2.1.1 Screening Failure

A screening failure is defined as a patient who has given informed consent and failed to meet at least one inclusion or exclusion criteria or has not been administered IMP as defined by the protocol.

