8.5.2.1.2 Re-Screening of Patients

Patients who fail to meet all inclusion/exclusion criteria will be permitted to be re-screened once at a later timepoint.

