8.7.1.2.2 Full Analysis Set (FAS)

The FAS includes all randomized subjects. The FAS serves as the primary efficacy analysis set (as randomized).

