3.1 Full Analysis Set (FAS)

The full analysis set (FAS) includes all randomized patients.

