4.9 Miscellaneous

For qualitative variables the frequencies (absolute and relative) are calculated. If no further remark is given in the description of the tables, following format will be used for all tables with qualitative variables (Note: In shift tables the percentages are based on the overall Total and not on the column Totals):

	Y-variable(s) (e.g., treatment group)					
	Category 1		Category 2		Total	
X-variable(s)	N	%	N	%	N	%
Category 1	xx	xx.x	xx	xx.x	xx	xx.x
Category 2	xx	xx.x	xx	xx.x	xx	xx.x
Missing	xx	xx.x	xx	xx.x	xx	xx.x
Total	xx	100.0	xx	100.0	xx	100.0

For this standard format the description of the tables in Appendix A determines only the X- and Y-variables. If another format of table is described in the details to the tables, the real design will be determined by the technical possibilities within SAS and may not look identical to the provided example. However, all information as displayed will be included.

Quantitative parameters will be described by declaring the mean value, standard deviation, minimum, first quartile, median, third quartile, and maximum. In the description of the tables this will be denoted by „basic statistics“. In general, minimum and maximum will be presented to the same level of precision as the raw data; means and medians, standard deviation, and quartiles will be presented to one further decimal place. P-values will be reported to four decimal places (i.e., 0.xxxx).

For frequency tables, all missing values (including user-defined missing values) will be combined in one category “missing” and included in the calculation of percentages. Percentages will be presented to one decimal place.

Tables and graphics will be presented only for scheduled visits.

The listings are always sorted by treatment group, center, and patient. If a different sorting order should be used for some listings this will be remarked separately. The variables for the special listings are explicitly given in the description of listings. All listings will be presented for the safety analysis set, if not stated differently, and indicator variables for further analysis sets, e.g., full analysis set, will be added if needed.

Enrolled but not treated patients (e.g. withdrawal before treatment) will be considered in tables and listings describing disposition of subjects, analysis sets as well as listings of PDs.

The following title will be used for all generated tables, listings, and graphs:

3570: APN01-01-COVID19 – final analysis

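### Two protocol rules, exclusion after an emergency code break and an open-ended definition of screening failure, conflict with the all-randomised full analysis set

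*Protocol*

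**What the plan says.** **Analysis set.** Protocol 8.7.1.2.2: "The FAS includes all randomized subjects". SAP 3.1 agrees: "The full analysis set (FAS) includes all randomized patients". Neither sets a dosing condition, and SAP 3.4 bases all efficacy analyses on this set.

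**Emergency unblinding.** Protocol 8.4.6 restricts unblinding to emergencies in which the treatment must be known to care for the patient, and then states: "Breaking of the emergency code leads to the exclusion of the respective patient". It does not say whether the exclusion is from dosing, follow-up or analysis.

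**Screening failure.** Protocol 8.5.2.1.1 applies the term to a consented patient who fails an inclusion or exclusion criterion "or has not been administered IMP as defined by the protocol". Neither limb is confined to the time before randomisation.

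**Re-screening.** Under Protocol 8.5.2.1.2, patients who fail the inclusion or exclusion criteria "will be permitted to be re-screened once at a later timepoint". Nothing restricts this to patients who were never randomised.

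**Untreated patients in the outputs.** SAP 4.9: "Enrolled but not treated patients (e.g. withdrawal before treatment) will be considered in tables and listings describing disposition of subjects", and the sentence continues to analysis sets and deviation listings. Efficacy outputs are not mentioned.

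**The concern.** Both rules act after allocation and can select on prognosis. An emergency code break happens because a patient is in trouble. A patient randomised but never dosed may have deteriorated first. The primary endpoint is death or invasive ventilation, so either group could be rich in events. If such patients leave follow-up or analysis, the groups compared are no longer the groups randomised.

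The screening-failure label matters because of what a site does with it. A record closed under that label gives little prompt to collect ventilation and vital status at Day 28. Serious adverse events are defined from first IMP administration (Protocol 8.5.2.2.13.2.2), so safety reporting is not a reliable back-up for an undosed patient. Neither document says how the primary endpoint is scored for a randomised patient recorded as a screening failure.

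**Working it through.** **1. Can a randomised patient meet the screening-failure definition?** Yes.
- Randomisation may be on Day -1 or Day 1, before treatment (Protocol 8.1).
- Exclusion 10 (haemoglobin) is judged at the time of infusion and exclusion 12 (pH or bicarbonate) before infusion starts (Protocol 8.3.2). Either can therefore fail after allocation.
- Randomised but untreated patients are expected (Protocol 8.7.2).
- The interval is short: start of screening to start of treatment may not exceed 24 hours (Protocol 8.5.2.1). Table 1 also waives the Day 1 criteria check if randomisation is on the screening day.

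**2. What does each text imply for these patients?**

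| Patient | FAS definition | Other rule |
|---|---|---|
| Randomised, code broken | in the FAS | excluded, set not named (8.4.6) |
| Randomised, never dosed | in the FAS | screening failure (8.5.2.1.1) |

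**3. How does the sample size treat untreated patients?** Inputs from Protocol 8.7.2: 50% vs 30%, two-sided alpha 0.05, 80% power, chi-squared test.

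n per group = [1.960·√(2·0.4·0.6) + 0.842·√(0.5·0.5 + 0.3·0.7)]² / 0.20² = 93.0, so 93 per group and 186 in total. This reproduces the plan's figure.

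The allowance is 200 − 186 = 14 patients, or 14/200 = 7.0%. Now assume 7 untreated per arm, with untreated APN01 patients at the 50% placebo rate:
- Untreated dropped: 93 per arm, 50% vs 30%, power 80.0%.
- Untreated kept, as the FAS requires: the APN01 rate is (93·0.30 + 7·0.50)/100 = 31.4%; with 100 per arm, power is 76.7%.

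The stated 80% is thus the figure obtained when the 14 do not contribute. SAP section 1 adds to the uncertainty by giving the planned size both as 200 treated and as 200 enrolled to cover the untreated.

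**4. How large could a bias be?** Nothing in the documents fixes it. As an extreme illustration, take 100 per arm, a 50% event rate in both arms, and k patients removed from one arm, all of them events. The expected shift is 0.5 − (50 − k)/(100 − k). The rejection rate is by exact enumeration of two Binomial(100, 0.5) counts, with Pearson chi-squared above 3.841.

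| Events removed (arm 1 / arm 2) | Shift, points | Rejection rate |
|---|---|---|
| 0 / 0 | 0 | 5.6% |
| 3 / 0 | 1.5 | 5.4% |
| 5 / 0 | 2.6 | 6.7% |
| 7 / 0 | 3.8 | 8.8% |
| 7 / 7 | 0 | 5.6% |
| 4 / 3 | – | 5.1% |
| 5 / 2 | – | 5.7% |

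At the planned rates, removing 7 events from the APN01 arm alone moves 30/100 = 30.0% to 23/93 = 24.7%. Inflation appears only when removals are both numerous and strongly one-sided.

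**The case against.** A reader might infer that the plan itself removes undosed patients from the primary analysis. The documents do not support that:
- Neither document gives screening failure any consequence for the analysis. Only the safety set, and the per-protocol set through it, depends on dosing.
- SAP 4.9 does not say that untreated patients appear only in the outputs it names. The paragraph before it makes the safety set the default for listings, so the sentence reads naturally as adding patients whom that default would omit.
- Protocol 8.3.3.1 asks for an end-of-study visit after withdrawal at any time, and 8.4.8.3 requires follow-up of enrolled patients who discontinue. Neither is limited to dosed patients.
- Under Protocol 8.7.1.2.5 and SAP 4.4.1, an early-terminated patient of unknown vital status counts as an event. If an undosed patient is recorded that way, lost status adds an event rather than deleting one.

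All of this stands. It leaves a gap: nothing says that a randomised patient labelled a screening failure counts as enrolled or as early terminated. If not, the follow-up duty and the worst-case rule do not clearly apply, and SAP 4.7 allows no imputation.

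Three further inferences also fail. Arm-selective withholding by the unblinded preparer is not shown: that person supplies a blinded dose and is given no decision on dosing. Double randomisation is not provided for: re-screening covers criteria failures only, although it does not expressly bar a randomised patient who fails one. Treating an incorrectly dosed patient as a screening failure is strained, since incorrect IMP use is handled as a major deviation leading to exclusion from the per-protocol set (SAP 3.3).

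On the code-break rule the defence is thinner. The sentence names no set, the SAP contains no matching FAS exclusion, and code breaking is not on its list of major deviations. Even so, the word is exclusion, and following it literally removes a randomised patient.

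**Conclusion.** The point holds as a conflict to be resolved and should be corrected. For code breaks, the protocol states a post-randomisation exclusion tied to clinical emergencies, and this cannot be squared with an all-randomised FAS unless it is confined to something other than follow-up and efficacy analysis. For undosed patients, the definition reaches past allocation, but the FAS definition, if followed, keeps them. The risk there is one of conduct: dropped records or lost Day 28 status. It is not a demonstrated removal.

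The size of any bias cannot be computed from the documents. The range from no inflation at 3 removals to about 8.8% at 7 assumes a 50% event rate in both arms and that every removal is an event in the same arm, so it is an extreme illustration and not an estimate. The 80.0% and 76.7% power figures assume 7 untreated per arm and a 50% rate in untreated APN01 patients.

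**What to change.** - **Protocol 8.4.6:** replace the exclusion sentence. An emergency code break is recorded as a protocol deviation, and the patient stays in follow-up and in the FAS.
- **Protocol 8.5.2.1.1:** define a screening failure as a consented patient who was not randomised, and delete the clause on IMP administration.
- **Protocol 8.5.2.1.2:** limit re-screening to patients never randomised.
- **Protocol 8.4.8.3:** state that randomised, undosed patients count as enrolled and have ventilation and vital status collected to Day 28.
- **SAP 4.9:** state that randomised, untreated patients are included in all FAS efficacy outputs.

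The cost is a few sentences across the two documents and a Day 28 status contact for a small number of patients; the plan's own allowance for untreated patients is 14 of 200.

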8.5.2.1.2 Re-Screening of Patients

Patients who fail to meet all inclusion/exclusion criteria will be permitted to be re-screened once at a later timepoint.

8.5.2.2 Study Examinations

Assessments are to be performed according to the schedule shown in Table 1.

On Day -1/1 of the study schedule the assessments have to be performed prior dosing.

Follow-up visit on Day 28 may be performed as a phone visit or in-home visit , where applicable . If a patient is already discharged from the hospital, the follow-up visits could be performed on an out-patient basis or at patient's home provided the patient agrees to that.

8.5.2.2.1 Safety

Safety will be evaluated by collecting reported AEs at regular intervals throughout the clinical trial and by the assessment of physical examination findings, vital signs, clinical laboratory parameters, and ECGs.

8.5.2.2.2 Medical and Medication History

A complete medical and medication history as well as demographic information will be assessed at Screening. The medical history will be reviewed and recorded, including:

Medical and Medication History for the least 4 weeks

- Relevant recent ingestion of medication
- History of respiratory, cardiovascular, renal, gastrointestinal, hepatic, endocrine, hematological, neurological, psychiatric, musculoskeletal and other diseases

Demographic information

- Date of Birth
- Sex
- Height and weight
- History of allergies
- History of smoking and alcohol use
- Body mass index (BMI)
- Ethnicity

8.5.2.2.3 Vital Signs

The vital signs will be reviewed and recorded, including:

- Temperature
- Heart rate
- Respiration
- Blood pressure
- Oxygen saturation.

Vital signs need to be tested before and after each dose.

All measurements of vital signs must be recorded in the appropriate source documents.

8.5.2.2.4 Physical Examination

A complete physical examination will be performed at the time points described in Table 1.

The physical examination will include a review of the following body systems:

- General appearance
- Skin
- Head, Eyes, Ears, Nose and Throat
- Spine/Neck/Thyroid
- Musculoskeletal
- Respiratory
- Cardiovascular
- Neurological
- Abdomen (including liver and kidneys).
- Relevant Co-Morbidities

Any abnormalities or changes in intensity from the screening visit noted during the review of body systems should be documented in the medical record. If a new clinically significant abnormal finding (i.e. not noted at baseline) occurs after screening has been completed, it must be captured as an AE and documented on the source documents. In addition, resolution of any abnormal findings during the clinical trial will be noted in the medical record if clinically significant.

Physical examination could also be documented in the context of the general visit/health status e.g. during a general clinical review assessment.

8.5.2.2.5 Pregnancy test

Appropriately performed using blood (serum) or urine test.

8.5.2.2.6 Clinical Laboratory Assessments

All laboratory assays will be performed according to the laboratory's normal procedures. Reference ranges will be supplied by the laboratory and used to assess the laboratory data for clinical significance and out-of-range pathological changes. The physician should assess out-of-range laboratory values for clinical significance, indicating if the value(s) is/are not clinically significant (NCS) or clinically significant (CS). Abnormal laboratory values that are unexpected or not explained by the patient's clinical condition may be, at the discretion of the investigator, PI or Sponsor, repeated until confirmed, explained, or resolved as soon as possible.

Details are defined in the Laboratory Manual. The following laboratory assessments will be performed:

Bio-Chemistry

Blood samples for biochemistry will be collected at the time points described in Table 1. The following parameters will be assessed:

Aspartate aminotransferase (AST)	Potassium (K)
Alanine aminotransferase (ALT)	Sodium (Na)
Alkaline phosphatase (AKP)	Albumin (ALB)
Total bilirubin (TBI)	Urea nitrogen (BUN)
Total protein (TP)	Creatinine (Cr)

Uric acid (UA)

eGFR (assessment is calculated according to the formula used in local laboratory)

Hematology / Blood Routine

Blood will be drawn at the time points described in Table 1. The following parameters will be assessed:

Red blood cell (RBC) count

Hemoglobin (Hb)

Hematocrit (HCT) or hematocrit total

Platelet (PLT) count

Classification of white blood cells (WBC)

Inflammatory Indicators

Blood will be drawn at the time points described in Table 1. The following parameters will be assessed:

C- reactive protein (CRP)

ESR

Procalcitonin

Urinalysis

pH (PH)

Urinary Protein (PRO)

Blood (red blood cells (BLD) and white blood cells (LEU))

Glucose (GLU)

Microscopic examination (if blood or protein is abnormal)

Stool routine and occult blood

The following parameters will be analyzed in fresh stool:

Red blood cells (RBC)

Occult blood

White blood cells (LEU)

Myocardial enzymes

The following parameters will be analyzed:

creatinine kinase (CK)

[alpha] - hydroxybutyrate dehydrogenase ([alpha]-HBD)

and isoenzyme (CKMB)

Troponin (cTnI)

lactate dehydrogenase (LDH)

Coagulation function

To assess the coagulation function, the following parameter will be analyzed:

Prothrombin time (PT)

D-dimer

Activated partial thromboplastin time (APTT)

FIB

Assessment of Immune function

To assess the immune function the following parameter will be analyzed:

COVID-19 Antibodies

Immunoglobulin (IgG, IgA, IgM)

Serology

During the screening period only, 1 or 2 blood samples will be drawn to test for the presence of HIV, HBsAg, and HCV antibody.

HIV testing (HIV I and HIV II) HCV antibody screen

HBV testing (HBsAg)

